## 8.2 SAFETY ASSESSMENTS

We plan to use the Patient Health Questionnaire-9 to monitor depressive symptom severity. PHQ-9 scores range from 0-27, with scores  $\geq 10$  indicating moderate-to-severe depression. Item 9 assesses “thoughts that you would be better off dead, or of hurting yourself in some way.” At screening, women with PHQ-9  $\geq 10$  or who endorse item 9 will be excluded from participation. Among enrolled participants, we will closely monitor depressive symptom severity and suicidal ideation via weekly administration of the PHQ-9. Qualified study personnel will make appropriate referral for community care for participants with PHQ-9  $\geq 10$ .

If a participant endorses the self-harm item of the PHQ-9, a pop-up will immediately appear with instructions to call 911 or go to the nearest emergency room for a life-threatening emergency. Additionally, email triggers will immediately notify study staff, who will call to conduct a risk assessment using the Columbia-Suicide Severity Rating Scale (C-SSRS).

At the beginning of the C-SSRS assessment, study staff will ask the participant for her current location. Study staff will provide psychological referrals for low to medium risk. For immediate risk, the study staff will direct the participant to the nearest emergency room and/or to call 911. If the participant declines, the study staff will call the participant’s local emergency services number, which will be recorded in the participant tracking database at enrollment. Study staff will immediately notify co-mentor [name], a psychiatrist with experience working with depressed and suicidal individuals, anytime a participant endorses suicidality on the PHQ-9. He will provide further supervision as deemed necessary and will determine whether additional follow-up assessment is indicated. Principal Investigator [name], a licensed clinical psychologist with experience working with depressed perinatal women, will be a back-up if [name] is unavailable.

Because suicidal impulses can change rapidly, participants will be instructed to make immediate contact with study personnel with any issues, questions, or concerns regarding worsening symptoms. At enrollment, we will provide contact information for [name], [name], local therapeutic resources, and crisis hotlines so that participants can have the phone numbers readily accessible.

## 8.3 ADVERSE EVENTS AND SERIOUS ADVERSE EVENTS

### 8.3.1 DEFINITION OF ADVERSE EVENTS

This protocol uses the definition of adverse events from the UCSF Clinical Research HUB: Adverse events are events that are undesirable and unintended, although not necessarily unexpected, effect of the research occurring in human subjects as a result of (a) the interventions and interactions used in the research; or (b) the collection of identifiable private information under the research.

### 8.3.2 DEFINITION OF SERIOUS ADVERSE EVENTS

A Serious Adverse Event is defined as any Adverse Event that results in any of the following outcomes:

- Death,
- Life-threatening adverse experience\*,
- Inpatient hospitalization or prolongation of existing hospitalization,
- Persistent or significant disability/incapacity,
- Congenital anomaly/birth defect, or cancer, or
- Any other experience that suggests a significant hazard, contraindication, side effect or precaution that may require medical or surgical intervention to prevent one of the outcomes listed above,
- Event that changes the risk/benefit ratio of the study.

\* A life-threatening adverse experience is any AE that places the patient or subject, in the view of the investigator, at immediate risk of death from the reaction as it occurred, i.e., it does not include a reaction that, had it occurred in a more severe form, might have caused death.

The events below are considered expected and will not be reported to the IRB:

- Increased sleepiness, which is a common short-term side effect of the sleep consolidation component of MBSR+PS
- Poorer sleep quality, which is normative as pregnancy advances

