## Specific Changes Implemented in Current Version

Description of Change	Brief Rationale
1. Include MBSR classes that are offered at locations in addition to UCSF Osher Center	1. A significant challenge is that the UCSF Osher Center does not offer MBSR frequently, and the classes fill up quickly. Currently, the number of eligible RISE Study participants exceeds the available spots in the Osher MBSR class. Additionally, we have had otherwise eligible study participants who were unable to participate because they were not available at the particular time of the Osher MBSR class
2. Add recruitment sources	2. To enable rapid identification of eligible participants and to maximize likelihood that we can achieve our anticipated accrual rate. We are having a lower yield from our Facebook ads compared to our previous studies. We are adding recruitment sources that we found helpful in previous studies, such as parenting listservs and social media posts
3. Remove Epworth Sleepiness Scale	3. Initially we planned to use the Epworth to screen for narcolepsy. The Epworth has excluded 10% of respondents on our screener. Narcolepsy has a base rate of 0.05%. Thus, it is highly implausible that 10% of respondents had narcolepsy. Instead we believe the Epworth is identifying people with normative pregnancy-related sleepiness. Additionally, this measure is redundant with an item that assesses whether participants have been diagnosed with narcolepsy
4. Increase the gestational age range from 12-28 to 8-28.	4. We have had several potential participants who are experiencing significant sleep disruption, are interested in participating, but are less than 12 weeks pregnant (and will be too far along in their pregnancy for the next available MBSR course). This wider gestational age range is similar to our previous research, in which we evaluated digital CBT for prenatal insomnia, and enrolled participants at any point in pregnancy up until 28 weeks

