## 2.3 RISK/BENEFIT ASSESSMENT

### 2.3.1 KNOWN POTENTIAL RISKS

**MBSR+PS:** Participation in the study intervention carries minimal risk of emotional discomfort. It is possible that participants may experience injury or discomfort during mindful stretching and walking practice; however, such practices may also improve pain during pregnancy. Previous studies of mindfulness-based interventions, including in pregnant populations, demonstrate safety and acceptability, with no adverse events reported. Some participants may be advised to implement techniques designed to consolidate sleep. These techniques reduce the amount of time spent awake in bed, which increases sleep drive, and ultimately decreases sleep onset latency and wake after sleep onset. Participants may experience temporary increases in sleepiness during this component of treatment. Two previous trials that included this technique among pregnant women found no unanticipated serious adverse events. We are aware of no research to suggest that the proposed intervention would confer risk to fetal, obstetric, or infant outcomes. At this time, there is a paucity of other treatments specifically for pregnancy-related poor sleep quality. Pharmacotherapy is associated with adverse birth outcomes, and pregnant women prefer non-pharmacological treatments. Cognitive behavior therapy targets maladaptive sleep beliefs and behaviors that are unique to chronic insomnia, and it does not address pregnancy-related factors of poor sleep quality.

**Self-report questionnaires:** There are no known risks for completing the study questionnaires, though it is possible that participants may experience temporary discomfort from thinking about their physical symptoms, psychological responses, and sleep.

**Actigraphy (optional depending on COVID-19 guidelines; see Section 8.1):** There is no risk of injury from the wrist-actigraph to measure sleep, though it may feel like a slight inconvenience wearing a wrist device for 14 days. There may be a risk of allergy to the metal of the actigraph device.

**Confidentiality of data:** Although every reasonable effort will be taken, confidentiality on web-based surveys cannot be guaranteed. It is possible that information may be captured and used by others who are not associated with this study.

**Inconvenience:** There may be some burden associated with completing the questionnaires and attending intervention sessions.

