### 2.3.3 ASSESSMENT OF POTENTIAL RISKS AND BENEFITS

**MBSR+PS** Participants will be provided with a thorough description of the intervention prior to randomization, and notified that they can withdraw participation at any time without penalty. Given the physical and psychological consequences of poor sleep quality during pregnancy, we expect that the proposed intervention would be associated with improved outcomes. However, important precautions will be taken to minimize physical risks. Participants will be provided the American College of Obstetrics and Gynecology list of indicators to terminate exercise. Participants will be advised to stop the physical activity if these signs are present, and to contact their obstetric health care provider. We will ask participants to alert us if they experience an increase in daytime sleepiness, and will advise them about the risks of driving or doing any activity where severe sleepiness puts them at danger, and will instruct them to take naps if they feel sleepy.

**Self-report questionnaires:** Participants will be allowed to skip any questions they do not feel comfortable answering. One exception is that participants will be informed during the initial screening that skipping questions that are necessary for determining eligibility may preclude their ability to participate in the study. Additionally, because all questionnaires will be completed online, participants can complete them in a location and at a pace that feels comfortable to them.

**Actigraphy (optional depending on COVID-19 guidelines; see Section 8.1):** In case of allergy, participants can wear the monitor over their sleeve or use a wrist sports sweatband to protect their skin.

**Confidentiality:** All data will be handled with the utmost attention to participants' confidentiality. Participants will be assigned unique, coded, confidential identifiers that will be used to label all data forms, data entries, and questionnaires. The key linking the participants' identity to their unique coded identifier will be stored on a cloud-based collaboration tool that uses access controls and encryption, and is safe for storing protected health information. Access to all data will be limited to the PI and trained,

authorized study staff.

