- Disruptors of sleep (physical symptoms, anxiety/worry, mind racing)
- Psychological responses to nightly physical symptoms

Depending on local COVID-19 guidelines, we may also use wrist-actigraphy to assess our secondary clinical outcome, objective sleep behaviors (total sleep time, sleep latency, wake after sleep onset, number of awakenings, sleep efficiency). We will collect these data only if local guidelines permit research as usual. Sending and receiving the wrist actigraphs requires multiple trips per week to FedEx, and we do not want to risk staff safety to collect this secondary outcome. Further, we have adequate feasibility data collecting actigraphy data from 50 pregnant women in our preliminary research (Aim 1 of K23).

**Outcome measures:** Consistent with our preliminary research (Aim 1 of K23), we will collect data on nightly physical symptoms, psychological mediators, and sleep quality using retrospective, self-report measures. We received feedback from Aim 1 participants that completing these online measures was not burdensome, and we had no missing data.

- Pregnancy Symptoms Inventory previously adapted to measure nightly sleep disturbances
- Measures of psychological mediators:
  - Self-Compassion Scale - Short Form
  - Rumination-Reflection Questionnaire
  - Five Facet Mindfulness Questionnaire
  - Coping Strategy Scale
- Measures of sleep:
  - Pittsburgh Sleep Quality Index
  - Insomnia Severity Index
  - Dysfunctional Beliefs About Sleep
  - Measures for coping with sleep disturbances
  - Worry about sleep
- Other clinical outcomes:
  - Patient Health Questionnaire-9

- PROMIS 6-item anxiety measure
- Perceived Stress Scale
- Contemplative practices and stress management techniques

**Daily measures:** Participants randomized to MBSR+PS will be asked to complete a brief daily home practice measure and the consensus sleep diary from the first until the last intervention session.

**Weekly measures:** Participants will complete a depression measure (Patient Health Questionnaire-9) once per week from randomization until endpoint.

**Endpoint measures:** Participants will complete the same outcome measures as at the baseline timepoint, as well as the Client Satisfaction Questionnaire and adverse events questionnaire.

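### Increased sleepiness is the only side effect the plan calls common, yet neither arm has a named sleepiness scale and its capture is likely to be unequal between arms

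*Combined protocol and SAP*

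**What the plan says.** Sections 8.3.2 and 8.3.5 name two events that are expected and not sent to the IRB. One is "Increased sleepiness, which is a common short-term side effect of the sleep consolidation component of MBSR+PS". The other, poorer sleep quality, is attributed to advancing pregnancy and not to the intervention.

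Section 2.3.1 explains the source: "Some participants may be advised to implement techniques designed to consolidate sleep", with temporary sleepiness as a possible result. Section 2.3.3, under its MBSR+PS heading, adds: "We will ask participants to alert us if they experience an increase in daytime sleepiness". The same paragraph covers advice about driving and other activities where sleepiness is dangerous.

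On scheduled capture, Section 8.1 says of the endpoint visit: "Participants will complete the same outcome measures as at the baseline timepoint, as well as the Client Satisfaction Questionnaire and adverse events questionnaire". The Schedule of Activities (Section 1.3) does not restrict that questionnaire to one arm. Section 8.3.4 says the endpoint inquiry covers the time since randomization and that events are documented whatever their relationship to the study. The items of the questionnaire are not given.

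The outcome lists in Section 8.1 name no sleepiness scale, and Section 8.2 covers only the PHQ-9 and suicidality. Section 9.4.4 (Safety Analyses) reads N/A. Section 10.1.6 has the Independent Monitoring Committee assess safety and efficacy data from each arm at least twice a year.

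**The concern.** The plan predicts a specific unwanted effect of one part of the intervention and treats it as a safety matter. It also accepts that pregnancy itself causes sleepiness. A count from MBSR+PS women alone therefore cannot show what the intervention adds. That needs the same question, asked in the same way and at the same times, in both arms.

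The plan does not arrange this. Women in MBSR+PS are asked to report sleepiness as it happens, and no matching request to TAU women is described. The one inquiry common to both arms comes at the end and looks back over the whole period, which suits a short-lived effect badly. At stake is the by-arm safety information that the monitoring committee will see and that the next trial will plan from. The primary objectives (acceptability, feasibility and adherence) are not affected.

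**Working it through.** **1. The plan's own figure.** Sections 5.5 and 9.2: 50 randomized × 0.80 retention = 40 with endpoint data. This reproduces. With 1:1 allocation (assumed, because the ratio is not stated) that is 20 per arm, or 25 per arm if no one is lost.

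**2. What each arm is asked, and when.**

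| Time | MBSR+PS | TAU |
|---|---|---|
| Baseline | no named sleepiness scale | no named sleepiness scale |
| During the course | weekly PHQ-9; daily sleep diary and home practice survey; request to alert staff to more sleepiness | weekly PHQ-9 |
| Endpoint | adverse events questionnaire | adverse events questionnaire |

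Sources: Sections 1.3, 2.3.3 and 8.1. The documents do not give the items of the diary, the sleep questionnaires or the adverse events questionnaire, so none is assumed to include or omit sleepiness.

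**3. Effect of unequal prompting.** Let p be the true proportion with increased sleepiness and s the probability that it is recorded, with subscripts M (MBSR+PS) and T (TAU). The expected recorded difference is p_M·s_M − p_T·s_T. If the intervention adds nothing (p_M = p_T = p), this becomes p·(s_M − s_T), which is above zero whenever MBSR+PS women are prompted more. Its upper bound is p: 10 to 30 percentage points for an assumed p of 10% to 30%. If instead both arms rely on late recall and s is low in both, a real difference shrinks. The error can therefore go either way.

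**4. Timing.** Section 9.2 places endpoint data at 8 weeks after randomization, and Section 1.3 allows 4 weeks either side. For an episode in week w, the recall gap is 8 − w weeks at the nominal date and 12 − w at the late edge. For an assumed w = 3, that is 5 and 9 weeks. The documents do not say when sleep consolidation is introduced.

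**5. Women with no inquiry.** The questionnaire is an endpoint measure. At 80% retention, 50 − 40 = 10 women would not reach it.

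**6. Baseline.** Section 8.3.4 treats conditions present at screening as baseline and records only deterioration. With no baseline sleepiness value, deterioration rests on the woman's own recollection.

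**7. What a common measure would give.** The 95% confidence interval half-width for a difference in means is t(0.975, 2n − 2) × √(2/n) SD. The difference detectable with 80% power (two-sided 5%, both assumed) is (1.960 + 0.842) × √(2/n) SD.

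- n = 20: half-width 2.024 × 0.316 = 0.64 SD; detectable 2.802 × 0.316 = 0.89 SD.
- n = 25: half-width 2.011 × 0.283 = 0.57 SD; detectable 2.802 × 0.283 = 0.79 SD.

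For a yes/no outcome at an assumed 10% (TAU) against 30% (MBSR+PS), the half-width is 1.96 × √[(0.10 × 0.90 + 0.30 × 0.70)/n]. That is 24 percentage points at n = 20 and 21 at n = 25, with power of 35% and 42%. At n = 20, the MBSR+PS rate detectable with 80% power is about 49%, 62% or 73% for an assumed TAU rate of 10%, 20% or 30%.

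**The case against.** The strongest reply is that capture exists in both arms. The endpoint questionnaire goes to everyone, events are documented regardless of relationship, and the exemption in Sections 8.3.2 and 8.3.5 concerns IRB reporting only, not recording. The trial is a feasibility pilot that Section 9.4.3 says is not powered for group differences, and step 7 shows that a common scale would still give an imprecise answer. Prenatal sleep sessions are recorded (Section 6.2.1) and attendance is logged (Section 6.4), so some of who heard the consolidation advice could be recovered. All of this stands, and it limits the point to a modest one. It does not remove the one-arm prompting or the single late inquiry. Imprecision is a reason to report descriptively. It does not excuse unequal ascertainment, which biases the comparison at any sample size.

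Four stronger readings are tempting, and the documents do not support them.

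- A reader might infer from the summary of changes ("Remove Epworth Sleepiness Scale") that the amendment created the gap. The stated role was different: "Initially we planned to use the Epworth to screen for narcolepsy". Nothing makes the Epworth a follow-up or safety measure.
- A reader might infer that neither arm has any scheduled capture. The endpoint questionnaire contradicts this, and its items may include sleepiness.
- A reader might infer that the effect cannot be separated from pregnancy sleepiness. TAU women share that background, so a comparison is valid if elicitation is equal.
- A reader might use "The Epworth has excluded 10% of respondents on our screener" to predict how many background reports to expect in MBSR+PS. That figure is the share above a screening threshold, whereas alerts concern an increase from a woman's own level. Women above the threshold were also excluded while the screen was in use.

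**Conclusion.** The point holds in a limited form. The one side effect called common has no named scale and no baseline value. Scheduled inquiry is a single retrospective questionnaire at endpoint, prompting during the course is described for MBSR+PS only, and no safety analysis is planned. Ascertainment is likely to be unequal and poorly timed, so by-arm data could overstate or understate the added sleepiness. The documents do not allow the size of that error to be computed; the bound in step 3 depends on an assumed background of 10% to 30%.

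The conclusion assumes that no equivalent prompt to TAU women exists outside these documents. It would weaken if the endpoint questionnaire asks about sleepiness specifically, though the timing and baseline problems would remain. This is a worthwhile low-cost improvement and not a defect in the primary objectives.

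**What to change.** Ask one identical sleepiness item, or a short scale, in both arms at baseline, in the weekly survey alongside the PHQ-9, and at endpoint. State that it does not affect eligibility. Add it to the Section 1.3 table and the Section 8.1 lists. Replace the N/A in Section 9.4.4 with a descriptive table by arm and time, giving differences with 95% confidence intervals and no claim of a test, and provide the same table to the monitoring committee.

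Optionally, add a log field for the prenatal sleep instructor showing which women received sleep-consolidation advice and in which week. That subgroup exists in one arm only, so it can be described but not compared with TAU.

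The cost is about 1 + 8 + 1 = 10 short answers per woman for a single item over 8 weeks, in surveys both arms already receive, plus one log field if adopted. No extra staff or visits are needed. The estimate will remain imprecise at this sample size, and the report should say so.

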### 8.3.3 CLASSIFICATION OF AN ADVERSE EVENT

### 8.3.3.1 SEVERITY OF EVENT

Adverse events will be assessed by the principal investigator with co-investigator [name], who has experience assessing psychiatric adverse events, and/or co-investigator [name], who has experience assessing medical adverse events. The following guidelines will be used to describe severity.

- **Mild:** Events require minimal or no treatment and do not interfere with the participant's daily activities.
- **Moderate:** Events result in a low level of inconvenience or concern with the therapeutic measures. Moderate events may cause some interference with functioning.
- **Severe:** Events interrupt a participant's usual daily activity and may require systemic drug therapy or other treatment. Severe events are usually potentially life-threatening or incapacitating. Of note, the term "severe" does not necessarily equate to "serious".

### 8.3.3.2 RELATIONSHIP TO STUDY INTERVENTION/EXPERIMENTAL MANIPULATION

All adverse events (AEs) will have their relationship to study procedures, including the intervention, assessed by an appropriately-trained clinician based on temporal relationship and his/her clinical judgment. The degree of certainty about causality will be graded using the categories below.

- **Definitely related:** An AE is definitely related to study participation if it is clear that the event was caused by study participation. A definitely related event has a strong temporal relationship and an alternative cause is unlikely.
- **Probably related:** An AE is probably related when there is a reasonable possibility that the event is likely to have been caused by study participation. The AE has a timely relationship to the study procedure(s) and follows a known pattern of response, but a potential alternative cause may be present.
- **Possibly related:** An AE is possibly related when there is a reasonable possibility that the event might have been caused by study participation. A possibly related event may follow no known pattern of response and an alternative cause seems more likely. In other circumstances there may be significant uncertainty about the cause of the event, or a possible relationship to study participation cannot reasonably be ruled out.
- **Unrelated:** The cause of the AE is known and the event is in no way related to any aspect of study participation. If there is any uncertainty regarding AE causality then the event must be assessed as possibly related to research participation and reported to the IRB as indicated. Often, the cause of an unrelated AE is disease progression.

